2.9 How will the outcome measures be measured at follow-up?

In MACS-5, clinicians who specialise in the follow-up of at-risk children are responsible for completing all assessments. They will determine the presence of cerebral palsy or other neurologic deficit, visual or hearing impairment (new or previously diagnosed), and undertake measures of growth (weight, height, head circumference) and blood pressure. The local research staff co-ordinate the visits and ensure that appropriately qualified clinicians are available to assess the children. Parents complete the BRIEF-P and the CBCL–Parent Form prior to or at the time of the visit, assisted by local research staff when necessary (see section 2.8.1).

For children in English-speaking centres, certified psychologists/psychometrists will test the children directly for the WPPSI-III, the Beery, and the Peabody Picture Vocabulary Test (see section 2.8.2).

2.10 Will health service research issues be addressed?

An economic analysis will be undertaken as part of *MACS* but is not planned as part of *MACS-5*.

2.11 Sample size and what is the justification for the assumptions underlying the power calculations

[figure not shown]
2.11.1 Sample size for primary outcome: death or survival with a severe disability in at least one of the following domains: neuromotor (non-ambulatory cerebral palsy), neurosensory (blindness, deafness, or need for visual and/or hearing aids), or neurocognitive (abnormal attention, memory or behaviour) function

The sample size of *MACS* is 1900 women. This sample size has an 80% power of finding a 33.3% reduction in the risk of RDS from 12% to 8% (2-sided Type I error of 5%), and greater than 80% power to detect an increase in the incidence of death or neurologic impairment from 5% to 9% at 18 to 24 months corrected age, if such a difference exists (2-sided Type I error of 5%).

We estimate that the children of 55% to 70% of mothers recruited to *MACS* will actually be followed to 5 years of age (or known to have died before this age) (N=1045-1330). This is based on an estimate that 70% to 90% of mothers in *MACS* will be recruited in centres participating in the 5 year follow-up, and that 80% of the children of these mothers will be followed to 5 years of age.

The primary outcome is a single binary variable, which is “abnormal” for a pregnancy if any child from that pregnancy meets any of the criteria given in Section 2.8.2. We do not know what the risk of an abnormal outcome will be in the placebo group at 5 years of age. However, the Cochrane Review of RCTs of a single course of ACS reports that in the treatment groups, the risk of neonatal death in babies treated after 1980 was 0.084 and the risk of long-term neurological abnormality among survivors was 0.057.⁷ Therefore, we assume that the risk of death or neurodevelopmental morbidity or abnormal cognitive skills (primary outcome) in the placebo arm at 5 years of age is 0.14. Four power curves for the primary outcome, assuming 55%, 60%, 65% or 70% follow-up, are given in Figure 2.11.1. A 2-sided type I error of 5% is used. The range of differences for which we would have an 80% power is 0.059 to 0.067, corresponding to a number needed to treat of 17 to 15. Since we expect to get more than 55%, and perhaps as much as 70%, follow-up at 5 years, we have adequate power for a difference in the range of 0.059 to 0.067, meaning that if physicians are willing to treat up to 15 or 17 patients to prevent an abnormal outcome, then we have sufficient power.

[figure not shown]
Figure 2.11.1 Power Curves for Primary Outcome

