2.8 Primary and Secondary Outcomes

2.8.1 Primary outcome for *MACS-5*: The primary outcome, to be assessed in all children at 5 years of age, is death or survival with a severe disability in at least one of the following domains:

neuromotor (non-ambulatory cerebral palsy), neurosensory (blindness, deafness, or need for visual and/or hearing aids), or neurocognitive (abnormal attention, memory or behaviour) function. Although the principal goal of **MACS-5** is to evaluate neurocognitive function at 5 years of age, as most surviving children with neuromotor and neurosensory disability will be identified before this time, it is important that the primary outcome is comprehensive, thus categorising all children with severe disability as abnormal.

1. *Death* is defined as any death prior to 5 years of age
2. *Neuromotor disability* is non-ambulatory cerebral palsy, to be determined by physical examination and the Gross Motor Function Classification System (GMFCS).⁴⁴ The GMFCS is a functional as opposed to a physiological or anatomical measure of cerebral palsy based on the child's ability to achieve independent ambulation. Non-ambulatory cerebral palsy is cerebral palsy that is at a GMFCS level of III, IV or V.
3. *Neurosensory disability* is defined as blindness, deafness or the need for visual and/or hearing aids.
4. *Neurocognitive disability (abnormal attention, memory or behaviour)* is defined as an abnormal score on either the BRIEF-P^{45,46} or the CBCL^{47,48} (see 4i and 4ii below).

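### Section 2.11.1 plans on two base rates that cannot both hold for MACS women, and its 0.14 placebo risk contains no term for abnormal attention, memory or behaviour

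*Protocol*

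**What the plan says.** Section 2.11.1 makes two power statements.

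- **Parent trial.** "The sample size of *MACS* is 1900 women", with power above 80% to detect "an increase in the incidence of death or neurologic impairment from 5% to 9% at 18 to 24 months corrected age". The word placebo is not attached to the 5%, but it is the rate from which the increase is measured, so it is the comparator risk.
- **5-year follow-up.** The protocol admits that the placebo risk is unknown. It then cites treatment groups in a review of single-course trials: "the risk of neonatal death in babies treated after 1980 was 0.084 and the risk of long-term neurological abnormality among survivors was 0.057". From these it draws a placebo-arm risk of 0.14 for the whole primary outcome, and concludes: "The range of differences for which we would have an 80% power is 0.059 to 0.067". It gives the matching number needed to treat as 17 to 15.

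Three other sections bear on this. Section 2.15.1 describes the 5-year pregnancies as a sub-sample of the parent trial's pregnancies. Section 2.8.1 counts a child as abnormal for death, non-ambulatory cerebral palsy, neurosensory disability, or an abnormal BRIEF-P or CBCL score, each cut at 1.5 SD above the normative mean. It also says that "most surviving children with neuromotor and neurosensory disability will be identified before this time", meaning before 5 years.

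**The concern.** A composite that includes death by 18-24 months cannot be rarer than neonatal death. If 5% holds for the composite, 8.4% cannot hold for neonatal death in these women. If 8.4% holds, the composite is at least 8.4%. Later follow-up does not explain the gap: neonatal death does not depend on the age at assessment, and section 2.8.1 expects most motor and sensory disability to be known before 5 years.

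The review figures come from single-course trials in general. The parent trial enrols women still pregnant 14-21 days after their course (section 2.5), and the protocol does not argue that the figures carry over.

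The second weakness is that the 0.14 is presented as the risk of the full primary outcome but is filled entirely by death and neurological abnormality. The neurocognitive component, which section 2.8.1 calls the principal goal of the follow-up, contributes no rate of its own. The detectable range and the number needed to treat rest on that 0.14, so a reader cannot tell what risk they really refer to.

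**Working it through.** **Inputs.** From section 2.11.1: 1900 women; 12% vs 8% and 5% vs 9%; 0.084, 0.057 and 0.14; N = 1045 to 1330; two-sided 5%. The allocation ratio is not stated, so 1:1 is assumed. Section 2.15.1 names Fisher's exact test, so I use the continuity-corrected formula per arm:

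n₀ = [1.96·√(2p̄(1−p̄)) + z_power·√(p₁(1−p₁)+p₂(1−p₂))]² / d², then n = (n₀/4)·[1+√(1+4/(n₀d))]²

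where d = |p₁−p₂| and p̄ is their mean.

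**Step 1: reproduce the plan's figures.**
- Parent trial, 950 per arm: 12% vs 8% gives 81% power; 5% vs 9% gives 91%. Both agree with the text.
- 5-year outcome from 0.14, as an increase at 80% power: 0.0591 at N = 1330 and 0.0675 at N = 1045. Exact Fisher enumeration gives 0.0590 and 0.0673. The text has 0.059 and 0.067.
- 1/0.059 = 16.9 and 1/0.067 = 14.9, the stated 17 and 15.

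Each statement works on its own input. The fault lies in the inputs.

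**Step 2: where 0.14 comes from.** Among survivors: 0.084 + (1 − 0.084) × 0.057 = 0.136. Simple sum: 0.084 + 0.057 = 0.141. Both round to 0.14, which leaves no room for a further component.

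**Step 3: test consistency.** Neonatal death 8.4% ≤ death or impairment by 18-24 months = 5% is false, by at least 3.4 points. If the review figures held, a 4-point increase with 950 per arm would have 79% power from 8.4% and 65% from 13.6%, against 91% from 5%.

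**Step 4: illustrate a total with a neurocognitive term.** Assumptions, none from the documents: scores are normal, children match the norms, and abnormal scores are independent of death or impairment. Beyond 1.5 SD lie 6.68% per scale. Either scale is then abnormal in 6.68% (complete overlap) to 1 − 0.9332² = 12.9% (independent scales). With base risk b and neurocognitive risk a, the total is b + (1 − b)a.

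| b | a | Total | Detectable increase, N = 1330 to 1045 | Reciprocal |
|---|---|---|---|---|
| 0.05 | 0.0668 | 0.113 | 0.055 to 0.063 | 18 to 16 |
| 0.05 | 0.1292 | 0.173 | 0.063 to 0.072 | 16 to 14 |
| 0.1362 | 0.0668 | 0.194 | 0.066 to 0.075 | 15 to 13 |
| 0.1362 | 0.1292 | 0.248 | 0.071 to 0.080 | 14 to 12 |

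The stated values, from 0.14, are 0.059 to 0.067 and 17 to 15.

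**The case against.** The best defence is that 0.14 is a declared proxy. The protocol says that the risk is unknown, never states 8.4% as a component rate in its own women, and applies only the total to a broader and later composite. The 5% belongs to the parent trial's planning and enters no 5-year calculation. Moreover, 5% plus a norm-based neurocognitive rate gives about 0.11-0.17, which brackets 0.14.

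Much of this stands. It shows that 0.14 may be near the truth. It does not rescue the derivation: the protocol reaches 0.14 as a consequence of the two review figures, not by adding a neurocognitive rate to 5%.

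Counting by pregnancy is a weaker defence. For a given number of fetuses, counting a pregnancy as abnormal if any child is abnormal cannot lower the risk. Only deaths concentrated heavily in multiple pregnancies, and shared by their babies, could reverse that. The protocol claims no such pattern.

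A reader might infer three stronger things that the documents do not support.

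- **That the primary outcome's placebo risk could be 0.05.** The 5% covers only death or neurologic impairment. Setting it against 0.14 as a 2.8-fold gap in the primary outcome compares a part with the whole.
- **That a reduction of 0.059-0.067 is impossible.** The power statement concerns the full composite, not the two components alone, and the range reproduces only as an increase.
- **That the trial is underpowered.** A lower base risk makes the detectable absolute difference smaller.

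**Conclusion.** The inconsistency holds. Within one subsection, 5% for death or neurologic impairment and 8.4% for neonatal death are planning rates that cannot both apply to the same women, and the 0.14 is built without the neurocognitive component. The documents do not show which rate is right.

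The effect on power is modest. Under the Step 4 assumptions, starting from 5% moves the detectable increase from the stated 0.059-0.067 to between 0.055-0.063 and 0.063-0.072. Starting from 13.6% moves it to between 0.066-0.075 and 0.071-0.080. The result can be slightly better or somewhat worse than stated. These figures assume 1:1 allocation and are illustrations, not estimates for this population: children born preterm may not match the norms, and abnormal scores may cluster with impairment.

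**What to change.** In section 2.11.1:

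1. Use one reconciled rate for death or neurologic impairment in both paragraphs, or explain why they differ. The masked pooled rate from the parent trial would be the natural source if it is available to the planners. The protocol reports no such rate, so its availability cannot be assumed.
2. Add an explicit rate for an abnormal BRIEF-P or CBCL score, with its source and the overlap assumed with the other components.
3. Restate the placebo risk, the detectable differences and the numbers needed to treat over the resulting range. Do not take 0.05 as the lower end, because it covers only part of the outcome.
4. Say whether each difference is an increase or a reduction. The present range matches an increase, while the text speaks of prevention. From 0.14, the same formula gives a detectable reduction of 0.050 to 0.057.

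The cost is one recalculation and some rewording, with no unmasking and no change to design or conduct. The stated power figures may become slightly less favourable.

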4ii) *Child Behavior Checklist (CBCL)-Parent Form*: The Parent Form for ages 1½-5 years is used as an additional measure of both attention and behavioural skills.^{47,48} This is one of the most commonly used tools to measure behaviours in children and has been used in studies evaluating behaviours in preterm children. The psychometric properties include high test-retest reliability (0.95-1.0), inter-rater reliability (0.93-0.96), and internal consistency (0.78-0.97) and validity estimates from .55 to .75. The CBCL has undergone numerous studies to assess content and construct validity. Comparisons with clinical status (referred/non-referred) also support the validity of the instrument.^{47,48} The Total Behaviors Problems T scores contributes to the primary outcome. An abnormal outcome is defined as a score that is 1.5 SD above the mean of the normative control sample; again, a higher score reflects abnormality.

The CBCL and BRIEF-P will be made available in all of the languages that are required for the study.

2.8.2 Secondary outcomes for MACS-5:

Secondary outcomes to be assessed in all children include *measures of growth and blood pressure*:

- 1i) height (cm)
- 1ii) weight (kg)
- 1iii) head circumference (cm)
- 1iv) systolic and diastolic blood pressure (mmHg)

Secondary outcomes to be assessed in children in English speaking centres include *intelligence and specific cognitive skills (visual motor, visual spatial, and language skills)*: For logistical reasons, only English-speaking centers that have trained psychologists or psychometrists that are available to administer these more specific psychological tests will participate in these assessments:

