2.15 Analysis

2.15.1 Analysis of primary outcome

Since the pregnancies used for the 5-year follow-up will be a sub-sample of the original *MACS* pregnancies, they will be compared to those not included with respect to the baseline variables: premature rupture of membranes (PROM), multiple birth (1 fetus versus 2+) and gestational age at randomisation. In addition, in the sample used for the 5-year follow-up, the treatment arms will be compared with respect to the same baseline variables. Fisher's exact tests will be used for PROM and multiple birth, and t-tests (or Mann-Whitney U test, if data are skewed) for gestational age. A two-sided Type I error of 0.05 will be used.

The primary outcome will be compared between treatment arms using a Fisher's exact test with a two-sided Type I error of 0.05. The relative risk and its corresponding 95% confidence interval will be calculated. In addition, a logistic regression analysis will be performed to compare treatment arms while controlling for PROM, multiple birth and gestational age. A multi-level model will be applied to the data using WinBUGS (version 1.4.1, see www.mrc-bsu.cam.ac.uk/bugs/welcome.shtml) to allow for random effects (intercept and slope) due to centres while also controlling for baseline variables. Using a similar analytic approach, a supportive analysis as described in the above four sentences will compare treatment arms with respect to the four domains comprising the primary outcome (death, neuromotor disability [non-ambulatory cerebral palsy], neurosensory disability [blindness, deafness, or need for visual and/or hearing aids], and abnormal cognitive score). Since pregnancy is the unit of analysis, if any child of a multiple birth has an abnormal outcome, the pregnancy will be considered to have had an abnormal outcome. If some of the data are missing, the child will only be considered to have an abnormal outcome if he or she is abnormal based on the data that are not missing.

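### The 0.14 placebo risk behind the primary-outcome power statement is used up by two baby-level figures and leaves nothing for the questionnaire component or the any-child rule, so 80% power for 0.059-0.067 is unsupported for the outcome as defined

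*Protocol*

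**What the plan says.** Protocol section 2.11.1 concedes that the placebo risk at 5 years is unknown. It then cites a review of single-course trials: "the risk of neonatal death in babies treated after 1980 was 0.084" and "the risk of long-term neurological abnormality among survivors was 0.057". The conclusion it draws from these two figures begins "we assume that the risk of death or neurodevelopmental morbidity or abnormal cognitive skills (primary outcome) in the placebo arm at 5 years", and the value it gives for the whole primary outcome "in the placebo arm at 5 years of age is 0.14". With 1045 to 1330 pregnancies followed and a two-sided 5% error, it claims 80% power for differences of 0.067 down to 0.059, and calls this adequate.

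The outcome in section 2.8.1 is wider than the two cited figures:
- It counts any death before age 5.
- It counts non-ambulatory cerebral palsy.
- It counts blindness, deafness or a need for visual or hearing aids.
- It counts neurocognitive disability, which "is defined as an abnormal score on either the BRIEF-P" or the CBCL. For each scale, "An abnormal outcome is defined as a score that is 1.5 SD above the mean of the normative control sample".

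Section 2.8.1 names neurocognitive function as the study's main aim. The unit is the pregnancy (section 2.15.1): "if any child of a multiple birth has an abnormal outcome, the pregnancy will be considered to have had an abnormal outcome".

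Section 2.11.1 also reports that the parent trial, MACS, was planned with more than 80% power for an "increase in the incidence of death or neurologic impairment from 5% to 9" per cent at 18 to 24 months.

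**The concern.** The component that MACS-5 chiefly exists to measure appears to have no share in the assumed event rate, and the rate is per baby although the analysis is per pregnancy. For a fixed absolute difference, power falls as the placebo risk rises from 0.14 towards one half, so omitted components would make the power statement too favourable. MACS-5 is meant to establish the safety of repeat courses. If the assumed rate is wrong, a null result could be read as excluding differences that the study was never shown able to detect.

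**Working it through.** **1. Where 0.14 comes from.** Simple sum: 0.084 + 0.057 = 0.141. Allowing for the second figure applying to survivors: 0.084 + 0.916 × 0.057 = 0.136. Both round to 0.14, so the two figures account for all of it.

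**2. Reproducing the stated differences.** With n = N/2 per arm (1:1 allocation assumed, as no ratio is stated) and d = |p2 − p1|:

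power = Φ{ [d − 1/n − 1.96·√(2p̄(1−p̄)/n)] / √[(p1(1−p1) + p2(1−p2))/n] }

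For N = 1330, n = 665, p1 = 0.14 and p2 = 0.199, p̄ is 0.1695. The numerator is 0.059 − 0.0015 − 0.0403 = 0.0172 and the denominator is 0.0205. The ratio is 0.837 and power is 0.80.

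Solving for 80% power gives an increase of 0.0591 at N = 1330 and 0.0675 at N = 1045, which matches the protocol. Exact Fisher power for the stated increases is 0.801 and 0.797. A decrease from 0.14 would give 0.050 and 0.056, so the stated range reproduces only as an increase.

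**3. The floor for the omitted questionnaires.** If scores are normal, P(Z > 1.5) = 0.067 on one scale. The chance of exceeding on either scale depends on their correlation: 0.067 (correlation 1), 0.099 (0.8), 0.115 (0.5), 0.129 (0). This assumes study children score no worse than the norm.

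**4. Adding only that floor.** p = base + (1 − base) × c, with c from 0.067 to 0.129 and the components independent:
- Base 0.136 (the protocol's two figures): 0.194 to 0.248 per child.
- Base 0.05 (the MACS planning value): 0.113 to 0.173 per child.

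**5. From child to pregnancy.** The documents give no twin rate. I assume 20% twins and a within-pair correlation of 0.3. The any-child risk is then p + 0.2 × 0.7 × p(1 − p). On the 5% base:
- 0.113 + 0.14 × 0.113 × 0.887 = 0.127
- 0.173 + 0.14 × 0.173 × 0.827 = 0.193

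That is about 0.13 to 0.19 per pregnancy, a range that contains 0.14. On the 0.136 base the same step gives 0.22 to 0.27.

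**6. Consequence.** The formula in step 2 gives the following. Each power cell shows N = 1045 with a difference of 0.067, then N = 1330 with 0.059. The last column runs from N = 1330 to N = 1045.

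| Placebo risk | Power, increase | Power, decrease | 80%-power increase |
|---|---|---|---|
| 0.13 | 81% / 82% | 95% / 94% | 0.058-0.066 |
| 0.14 | 79% / 80% | 93% / 92% | 0.059-0.067 |
| 0.19 | 72% / 72% | 83% / 82% | 0.065-0.074 |
| 0.20 | 70% / 70% | 81% / 80% | 0.066-0.076 |
| 0.25 | 65% / 65% | 73% / 72% | 0.071-0.081 |

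**The case against.** A reader might infer that 0.14 is shown to be too low and the study therefore underpowered. The documents do not support that, for three reasons.

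First, the base itself may be too high. MACS women are still pregnant 14-21 days after a first course with all fetuses alive (section 2.5), a different population from the trials behind 0.084. MACS itself planned on 5%. Rebuilt from 5%, the rate straddles 0.14. The 5% is only a planning value for an earlier age and a narrower outcome, so it does not strictly contradict 0.14, but the two figures sit in the same section without explanation.

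Second, direction matters. Section 2.11.1 speaks of treating patients to prevent an abnormal outcome. For a decrease, the stated differences keep about 80% power up to a placebo risk of roughly 0.20. The shortfall applies first to harm.

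Third, two tempting labels go too far. This is not an arithmetic error, because the calculation from 0.14 onward is correct. Nor is it shown that visual and hearing aids have zero weight: the protocol does not define the source's neurological abnormality, which may include some sensory loss.

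It is also fair that the sample is bounded by MACS enrolment and that the protocol admits the rate is unknown. All of this limits the size of the problem. It does not supply the missing derivation: a rate that may be right by coincidence does not support a power claim.

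**Conclusion.** The point holds as an unsupported planning input. The 0.14 gives no weight to abnormal BRIEF-P or CBCL scores, to deaths after the neonatal period, or to the any-child rule, and no stated rate covers visual or hearing aids. The 80% power claim for 0.059-0.067 is therefore not established for the outcome in section 2.8.1.

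The size is uncertain. Plausible rebuilt rates run from about 0.13 per pregnancy to 0.25 per child or slightly more per pregnancy. Over 0.13 to 0.25, power for the stated increases runs from about 82% down to 65%. For decreases it is 92-93% at 0.14, about 80% at 0.20 and about 72% at 0.25. These figures assume normally distributed scores, no excess over the norm in study children, independent components, 1:1 allocation and, where used, the twin assumptions above. Any excess of high scores in preterm children, or use of visual or hearing aids beyond the cited figures, would raise the rate.

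This should be fixed, but it does not threaten the design: no outcome, test or sample size depends on it.

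**What to change.** In section 2.11.1, rebuild the placebo rate per pregnancy from the actual components:
- death to age 5, non-ambulatory cerebral palsy and sensory disability, from blinded pooled MACS data where they exist (these may be partial, as MACS was still enrolling when the protocol was written);
- the exceedance rate of either questionnaire;
- visual and hearing aids;
- the any-child rule, with a stated multiple-birth rate.

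Explain how the result relates to the 5% planned for MACS. Then restate, in the text and in Figure 2.11.1, the differences with 80% power separately for an increase and a decrease, over placebo risks of about 0.13 to 0.30. For an increase these would be 0.066-0.076 at 0.20 and 0.071-0.081 at 0.25.

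The cost is one re-run calculation and probably a less favourable stated detectable difference. N is unchanged.
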